Based on effects reported in previous literature using a similar experimental paradigm and participant populations^{9, 10}, we anticipate that 30 participants per group (N=90 total) will provide sufficient power to test the primary study hypotheses. Therefore, this study will recruit 90 healthy men and women aged 18-85. Subjects will be identified and recruited through multiple approaches. Local University and community postings will be used to identify and recruit the healthy control participants. Additionally, partnerships with collaborators within the Division of Physical Therapy, Emory School of Medicine and Emory Healthcare will be utilized in subject identification and recruitment. Initial contact may be made by [name] or one of his associates.

Informed Consent. The letter of informed consent will be used as a template to describe what is being asked of the participant, the risks and benefits associated with participation etc. to the participant. The consent form will be explained by a member of the research team. At this time the individual making contact will also be available to answer any specific questions that may arise. Informed consent will be conducted by either [name] or a research coordinator in private-either in the research lab or a single-occupant office.

In testing sessions performed at the Neural Plasticity Research Laboratory (NPRL), participants will undergo: 1) noninvasive targeting of cortical locations by stereotactic neuronavigation using transcranial magnetic stimulation (TMS), 2) TMS measures of cortical excitability and neurotransmitter signaling, and 3) a motor learning paradigm. The duration of the testing session will be less than 3 hours. Participants may also be asked to complete a single magnetic resonance imaging (MRI) session prior to testing in the NPRL. Overall, participants will complete up to two study visits.

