Inclusion Criteria. This study utilizes non-invasive brain stimulation, which is associated with minimal risk. To further minimize any risks associated with the stimulation, every subject will be informed of the potential risks of participation in the consent form and will complete a form that screens for any potential factors that could increase risk. The PI will use this information to determine eligibility. Inclusion criteria include (1) no history of movement impairment or neurodegenerative disease (2) right handedness (3) no contraindication to transcranial magnetic stimulation (TMS)¹¹ or magnetic resonance imaging (MRI).

[figure not shown]

Figure 1. Experimental Design. Visit 1 will consist of a MRI session to acquire a structural image that will allow us to identify the target site of stimulation. Visit 2 will consist of a motor learning paradigm, during which one of three TMS conditions will be applied: premotor cortex (PMC) stimulation, primary motor cortex (M1) stimulation, or sham stimulation.

Exclusion Criteria. Any participant will be excluded if they: 1) are outside the age range of 18-85, 2) have a history of head trauma or neurodegenerative disorder, or 3) report contraindications

to TMS. Participants over age 65 will be asked to complete the Montreal Cognitive Assessment, and participants with a score of 25 or lower (out of the “normal” range) will be excluded.

Experimental Design: Participants will complete up to three study visits: a MRI session and a TMS session (**Figure 1**). During the TMS session, participants will be randomly assigned to receive one of three types of stimulation during the motor learning paradigm: TMS over premotor cortex (N=20), TMS over primary motor cortex (M1, N=20), or sham TMS over premotor cortex (N=20). Groups will be gender- and age- matched. Motor performance and cortical excitability will be assessed before and after the motor learning paradigm.

MRI Acquisition

Enrolled participants may complete a MRI scan prior to the experiment to obtain a structural brain image that will be used for guided navigation during TMS protocols. T1-weighted images will be acquired at the Center for Systems Imaging at Emory University on a Siemens Prisma 3T scanner (TR = 7.4ms, TE = 3.7ms, flip angle $\theta = 6^\circ$, 1 mm isotropic resolution, scan time=3.2min). Data will be stored on Emory University’s secure network server.

TMS Procedures

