A skill score (SS) will be calculated as the difference between performance on the random blocks minus the average performance on the patterned sequence in the test block to determine how well the patterned is learned. Percent change in SS will be used to index sequence-specific motor learning while controlling for general improvements in motor performance. One-way ANOVA will be used to test for differences in sequence-specific skill acquisition and sequence-specific skill retention between the groups that received different types of TMS stimulation. R statistical packages will be used for statistical analyses. Secondary statistical analyses will use a repeated measures ANOVA to examine differences in cortical excitability before and after motor training. Significance level will be set at $\alpha \leq 0.05$.

Compensation:

Participants will get \$20 for each completed study visit, to compensate them for their time and effort. If they do not finish the study, we will compensate them for the visits they have completed. They will get \$40 total if they complete two study visits.

Data Safety and Monitoring

To ensure safety and minimize risks to study subjects, the following data safety monitoring plan (DSMP) will be implemented in accordance with the Emory University IRB DSMP guidance document:

The primary risk for subjects participating in this study is the risk of seizure associated with transcranial magnetic stimulation (TMS). Although no seizures have been reported as a direct result of the type of stimulation in this study, to minimize any risk of seizure, we will not enroll individuals with a history of seizure. A TMS screening form (adapted from ¹¹) will be administered for each subject prior to beginning the study to identify potential factors that would place the subject at increased safety risk (e.g. epilepsy or epileptogenic medications).

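### The power claim rests on 30 participants per group (90 in total), but the design section randomises 20 per group (60 in total), and nothing reconciles the two

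*Combined protocol and SAP*

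**What the plan says.** The combined protocol and SAP gives the sample size in two places.

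- **Participants and Recruitment.** The power statement reads "we anticipate that 30 participants per group (N=90 total) will provide sufficient power to test the primary study hypotheses". The recruitment target follows from it: "Therefore, this study will recruit 90 healthy men and women aged 18-85". The stated basis is "Based on effects reported in previous literature using a similar experimental paradigm and participant populations", with two cited studies. No effect size, SD or numerical power is given.
- **Experimental Design.** Here "participants will be randomly assigned to receive one of three types of stimulation during the motor learning paradigm", and the arms are listed as "TMS over premotor cortex (N=20), TMS over primary motor cortex (M1, N=20), or sham TMS over premotor cortex (N=20"). No total is stated; the three arms add up to 60.

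The Statistical Plan gives no sample size, so it does not settle the matter. It names the primary test: "One-way ANOVA will be used to test for differences in sequence-specific skill acquisition and sequence-specific skill retention between the groups", with a significance level of 0.05.

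**The concern.** The only power statement in the document is attached to 30 per group, while the section that sets up the randomised arms gives 20 per group. A reader cannot tell which trial will be run, or whether the one that is run has the size claimed to be adequate.

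Two things are at stake. First, the main hypothesis is that premotor cortex is necessary for learning a motor skill, so a null result would be read as evidence against it. At 60 participants a null result is more likely to be a false negative than the power statement implies. Second, recruitment could end at 60 or at 90, each with support in the text and with no rule for choosing. That leaves room for the choice to be made after outcome data have been seen.

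**Working it through.** **1. The two totals.**

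- Participants and Recruitment: 3 × 30 = 90, which agrees with the stated total.
- Experimental Design: 3 × 20 = 60.
- Shortfall: (90 − 60)/90 = 33%.

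**2. Can 90 recruited and 60 randomised both be right?** Reading 90 as enrolled and 60 as completers needs a loss of 1 − 60/90 = one third, since 60/(1 − 1/3) = 90. Loss of 10% or 20% would give 60/0.9 = 67 or 60/0.8 = 75 enrolled. No loss rate is stated. The wording also blocks this reading: the 30 is a per-group figure tied to power, and the 20 is a number assigned, not a number analysed. Assignment takes place at a single session of under 3 hours, with retention tested 30 minutes after training, so heavy loss after assignment is not an obvious explanation. The MRI visit is optional and carries no failure allowance.

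**3. Can the plan's own figure be reproduced?** No. Without an effect size, SD and target power, 30 per group cannot be derived. The next steps assume a target power at 30 per group and work from there.

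**4. Power of the one-way ANOVA.** With k = 3 groups, n per group, N = 3n and alpha = 0.05, power is the probability that a noncentral F variable with 2 and N − 3 degrees of freedom and noncentrality λ = N f² exceeds the 95% point of the central F. Here f is the SD of the group means divided by the within-group SD. For the pattern in which the premotor group is lower by d SDs and the other two groups are equal, the means 0, 0, −d give f = d√2/3, so d = 3f/√2.

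| Assumed power at 30 per group | Implied f | Implied d | λ at N = 90 | λ at N = 60 | Power at 20 per group |
|---|---|---|---|---|---|
| 80% | 0.333 | 0.71 | 9.97 | 6.65 | 61% |
| 85% | 0.354 | 0.75 | 11.31 | 7.54 | 67% |
| 90% | 0.382 | 0.81 | 13.10 | 8.73 | 73% |
| 95% | 0.422 | 0.89 | 15.99 | 10.66 | 82% |

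The λ columns use f to four decimals (0.3329, 0.3545, 0.3815, 0.4215); for example, 90 × 0.3329² = 9.97 and 60 × 0.3329² = 6.65.

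**5. Cross-check with a two-sided t test between two groups.** If 30 per group gives 80% (d = 0.74), 20 per group gives 62%. If it gives 90% (d = 0.85), 20 per group gives 75%. The pattern is the same.

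**6. Detectable effect at 80% power.** At 30 per group f = 0.333, so d = 3 × 0.3329/√2 = 0.71. At 20 per group f = 0.412, so d = 3 × 0.4115/√2 = 0.87.

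**7. Power over a range of effects, with no assumed target.**

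| f | 30 per group | 20 per group |
|---|---|---|
| 0.25 | 54% | 37% |
| 0.30 | 71% | 51% |
| 0.35 | 84% | 65% |
| 0.40 | 93% | 78% |
| 0.50 | 99% | 93% |

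**8. Precision.** The standard error of a difference between two group means is σ√(2/n). The ratio of n = 20 to n = 30 is √(30/20) = 1.225, a 22% increase. This needs no effect-size assumption, only the same SD.

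**The case against.** The strongest reply is that 90 is the intended size and the 20s are leftover text. Participants and Recruitment states its size in three consistent ways (per group, total and number to recruit). The Experimental Design paragraph has another slip: it allows up to three visits but lists two, while Participants and Recruitment allows up to two and Compensation pays for two. If 90 governs, no power is lost and only the arm sizes are wrong. This is plausible, but the document does not establish it, and staff filling arms from the design paragraph would stop at 60.

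A second reply is that the power loss depends on an effect size nobody has stated. That is correct. With a large effect (f = 0.50), 20 per group would still give 93%. The 61% and 73% figures are therefore conditional, and only the 22% increase in standard error holds at any effect size.

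A third reply is that no interim look at outcome data is planned; the six-monthly reviews cover adverse events and data verification. That also stands. The text does not show that outcome data would influence when recruitment ends. It only lacks a rule that would prevent it.

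None of these replies removes the contradiction.

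**Conclusion.** The concern holds. The protocol gives two sample sizes that differ by one third, and its power claim applies only to the larger. The error could lie in either section.

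If the arms are filled to 20, power falls to about 61% when 30 per group was sized for 80%, or to about 73% when it was sized for 90%. Both figures assume the three-group ANOVA at alpha 0.05 and full data. In the 80% case the false-negative risk at the design effect rises from 20% to about 39% (1 − 0.607). Because sample size and power are figures on which the trial relies, this must be corrected and should not be treated as a clerical detail.

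**What to change.** State one sample size throughout.

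- **If 90 is intended:** change each of the three arm sizes in Experimental Design from 20 to 30. This is a one-line correction and needs no recruitment beyond the 90 already stated.
- **If 60 is intended:** change Participants and Recruitment to 20 per group and 60 in total, withdraw the power claim attached to 90, and state the effect detectable with 80% power (about f = 0.41, or 0.87 SD for a lower premotor group). The cost is a less favourable stated sensitivity.

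Under either option, add the assumed effect size and SD, the target power and any allowance for loss, and separate the number randomised from the number expected in the analysis. Without these, the power statement cannot be checked even at 90. A sentence saying that recruitment ends at the stated number, whatever the outcome data show, would close the remaining gap.

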Characterizing cortical contributions to motor sequence learning

Cortical contributions to motor sequence learning

[name], DPT, PhD. Division of Physical Therapy, Department of Rehabilitation Medicine, Emory School of Medicine

Protocol Version 1 9/20/2019

NCT04138953

Characterizing cortical contributions to motor sequence learning

Abstract:

The long-term objective initiated with this study is to determine which brain areas functionally contribute to learning a motor skill. Our primary hypothesis is that premotor cortex (PMC) is necessary to learn a new motor skill. Healthy adults (age 18-85) will be recruited to participate in this study at the Emory University Rehabilitation Hospital. Participants may undergo a MRI scan to acquire a structural image of their brain to target noninvasive stimulation, using transcranial magnetic stimulation (TMS) to one of two brain areas: PMC or primary motor cortex (M1). A third group of individuals will undergo a placebo stimulation protocol. For all three groups, stimulation will be used to create a transient 'virtual lesion' during motor skill training.

Temporarily disrupting the normal activity of these brain regions during training will allow us to determine which regions are causally involved in learning a new motor skill. The primary outcome measure will be the change in skill after training in each group. We anticipate the group receiving sham stimulation or stimulation to M1 will have greater increases in skill learning than the group receiving stimulation to PMC.

Introduction and Background:

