Guided navigation will be used throughout the session in real-time to ensure consistent spatial localization of TMS application. BrainSight software (Rogue Research Inc.) will be used to localize stimulation over the motor representation associated with the target muscle, which will be the first dorsal interosseous (FDI) muscle of the hand. Electromyography (EMG) will be used to measure TMS-motor evoked potentials (MEPs) of the FDI muscle during all testing conditions. The resting motor threshold (RMT) will be defined for each hemisphere as the stimulus intensity required to elicit a MEP response greater than $50\mu\text{V}$ in over 50% of trials.¹² During the motor learning paradigm, sham or real TMS pulses will be delivered over premotor cortex or M1 at a stimulation intensity of 80% RMT time-locked to the presentation of specific visual stimuli (described in further detail below). Before and after the motor task, participants will receive blocks of TMS at 120% RMT and between 30 and 80% of maximum stimulator output to create an input/output curve to evaluate cortical excitability.

Motor Sequence Learning Paradigm

A modified version of the serial reaction time task (SRTT)¹³ will be used to assess motor sequence learning in all study participants (**Figure 2**). During this task, the left hand will be placed on a button box so that the four fingers will press specified keys. Four colored squares will appear on the screen, and participants will be instructed to press the button that corresponds to a target square located beneath the four colored squares. The button presses will occur in a repeating pattern, and response time will be measured to indicate how well the pattern is learned. There will be blocks of random sequences at the beginning and end of the test blocks that will be used

[figure not shown]

Figure 2. Example trials of SRTT. Four boxes on the top of the screen correspond to four buttons on a button box. The target box on the bottom indicates which button to press. The colors change each trial so the participant cannot learn the sequence of colors.

to assess general task performance, and there will be five blocks in between that will be used to train the sequence. A follow-up block of the task will be performed 30 minutes following training to test short-term retention of skill.

Risks and Discomforts:

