Motor performance tests: There are no known risks associated with these tests. They may however be difficult at times, and if the participant becomes discouraged and would like to stop, they can tell the researcher.

Electroencephalography (EEG): Collection of EEG involves application of electrodes over the scalp to measure brain activity. All electrodes do not contact the skin. A gel provides the contact between the skin and the recording electrodes. In rare instances it is possible that the skin may be sensitive to the gel or rubbing alcohol used for surface recordings. In such cases a skin rash is possible. The conductive gel is water-soluble and washes out quickly with warm water and shampoo.

Transcranial magnetic stimulation (TMS): Safety standards for the application of TMS have been developed. Trained operators will follow these standards during this study to minimize the risk. The TMS machine will always be run at a rate and a frequency that are known to be safe. There is a potential risk of causing a seizure in people with a history of seizures (e.g. epilepsy); however, there has never been a report of a seizure associated with the type of TMS used in this study (i.e. single and double pulse TMS). Participants will not be eligible to participate in this study if they have a history of seizure. There is a possible small risk of headache, scalp pain, toothache or scalp numbness associated with single and double pulse TMS. Each of these side effects is transient (i.e. does not last). The clicks associated with single and double pulse TMS are loud and could potentially damage the participant's hearing with prolonged exposures. To minimize this risk, participants will be asked to wear earplugs during the testing session.

There may be other risks that have not yet been identified, and unexpected side effects that have not been previously observed may occur.

Statistical Plan:

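### Sham participants receive real TMS before training, neither the sham's sensation nor any check of perceived allocation is described, and the omnibus ANOVA cannot separate a PMC-specific deficit from a real-versus-sham difference

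*Combined protocol and SAP*

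**What the plan says.** The Abstract describes the control condition in one sentence: "A third group of individuals will undergo a placebo stimulation protocol". Experimental Design adds the coil site and group sizes: "TMS over primary motor cortex (M1, N=20), or sham TMS over premotor cortex (N=20". Nothing further is said about the sham, such as the coil or the matching of sound or scalp sensation.

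TMS Procedures sets the training stimulation: "sham or real TMS pulses will be delivered over premotor cortex or M1 at a stimulation intensity of 80% RMT". The same section applies excitability testing to everyone, with no exception for the sham arm: "Before and after the motor task, participants will receive blocks of TMS at 120% RMT and between 30 and 80% of maximum stimulator output". RMT is defined there by an evoked muscle response, so 120% RMT is above motor threshold. Participants and Recruitment puts TMS measures and motor learning in one testing session of under three hours.

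On what participants can perceive, Risks and Discomforts says "The clicks associated with single and double pulse TMS are loud" and "There is a possible small risk of headache, scalp pain, toothache or scalp numbness associated with single and double pulse TMS". Earplugs are specified there for hearing safety, not for masking. No section says who is blinded, or that participants are asked which stimulation they think they had.

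The Statistical Plan derives a skill score as random-block minus sequence performance, takes its percent change, and compares the three groups by one-way ANOVA for acquisition and for retention. No pairwise contrasts are named. The Abstract predicts that sham and M1 will each gain more skill than PMC.

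**The concern.** A sham participant meets real pulses earlier in the same visit and so has a recent reference for click and scalp sensation. If the sham does not reproduce these, sham participants may train with less distraction, or with different expectations, than participants in the two real arms. Skill is built from response times, which distraction or expectation could move. A lower gain under real stimulation would agree with the predicted PMC-sham direction without any disruption of PMC.

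The analysis does not resolve this. A significant omnibus F says that the three means differ somewhere. It does not say whether PMC stands apart or sham does. Without a record of sensation and belief, and without stated contrasts, the report would have little with which to argue for one reading over the other.

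**Working it through.** **Plan's own figure.** Participants and Recruitment states 30 per group (90 in total); Experimental Design states 20 per group (60). No effect size, SD or power is given, so neither can be reproduced, and the two sections need reconciling. Both sizes are used below. For orientation, the pairwise difference detectable with 80% power at two-sided 0.05 is (1.960 + 0.842) × √(2/n): 0.89 SD at n = 20 and 0.72 SD at n = 30.

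**Assumption.** There is no true PMC or M1 effect, but sensation or awareness lowers skill gain by b SD under real pulses. The documents give no value for b; 0.2, 0.3 and 0.5 are illustrative.

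**Omnibus F.** The noncentrality is λ = n × Σ(μᵢ − μ̄)².
- Shift in PMC only, means (−b, 0, 0): the mean is −b/3, and the sum of squares is (4/9 + 1/9 + 1/9)b² = (2/3)b².
- Shift in both real arms, means (−b, −b, 0): the mean is −2b/3, and the sum of squares is (1/9 + 1/9 + 4/9)b² = (2/3)b².

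The two patterns give the same λ and therefore the same rejection rate. For b = 0.5, λ = 20 × 0.25 × 2/3 = 3.33 at n = 20, and 30 × 0.25 × 2/3 = 5.0 at n = 30. The degrees of freedom are 2 and 3n − 3.

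**PMC-sham t-test.** Noncentrality b√(n/2), with 2n − 2 degrees of freedom, two-sided 0.05. The plan does not name this test; it is shown for comparison.

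**Full predicted pattern.** The chance that PMC is significantly below both sham and M1 when both real arms are shifted equally, by simulation (100,000 trials per cell, so the last digit is approximate).

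| n per arm | b (SD, assumed) | ANOVA rejects, either pattern | PMC-sham t-test rejects | PMC below both sham and M1 |
|---|---|---|---|---|
| 20 | 0.2 | 9.0% | 9.5% | 1.1% |
| 20 | 0.3 | 14.5% | 15.2% | 1.5% |
| 20 | 0.5 | 33.7% | 33.8% | 2.0% |
| 30 | 0.2 | 11.3% | 11.9% | 1.2% |
| 30 | 0.3 | 20.1% | 20.8% | 1.7% |
| 30 | 0.5 | 48.9% | 47.8% | 2.3% |

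The first two rates exceed the nominal 5% and rise with sample size. The last column stays near 1% to 2%, because an equal shift cancels between PMC and M1.

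**Precision of a guess question.** Near 50% correct, the 95% half-width is 1.96 × √(0.25/n): 22 percentage points at n = 20 and 18 at n = 30.

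**The case against.** Four points on the other side have weight.

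1. **Training intensity.** Training pulses are at 80% RMT, below motor threshold, while the pre-task reference includes 120% RMT. Real and sham training pulses should both seem weaker than those test pulses, so noticing a drop does not identify sham. This stands as a limit on size. It does not close the gap: RMT concerns the muscle response, not click or scalp sensation, and the input/output curve may include lower intensities.
2. **The skill score.** Subtracting sequence from random-block performance removes general slowing. That holds if pulses fall alike in both kinds of block. TMS Procedures promises the pulse timing later in the document, and it is not given. The subtraction would also not remove an effect of distraction on learning itself.
3. **The M1 arm.** It receives real pulses at the same percentage of RMT, and a non-specific effect contradicts the M1 half of the prediction. This is the strongest point. A reader might infer that the trial could never show a PMC deficit to be neural; the design does not support that, because PMC versus M1 bears on it, subject to differences in sensation by site. What remains is that the plan does not name the contrast.
4. **Blinding.** A reader might infer that participants are unblinded. The words sham and placebo imply an intention to conceal, and the consent pages, which might show what participants are told, are not in the public copy. The most that can be said is that no blinding, sham matching or belief check is described.

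It would also go too far to say that participants in the real arms train with scalp discomfort. The protocol gives scalp pain or numbness only as a small possible risk, and says nothing of sensation at 80% RMT.

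**Conclusion.** The concern holds in a limited form. Sham participants receive real TMS above motor threshold before training, the documents describe neither how the sham reproduces click and scalp sensation nor any check of perceived allocation, and the omnibus ANOVA treats a PMC-specific deficit and a shared real-versus-sham deficit identically. That last statement follows from the algebra and needs no assumed effect size.

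The size of any bias is unknown. The ANOVA rates of 9% to 34% (20 per arm) and 11% to 49% (30 per arm) rest wholly on an assumed shift of 0.2 to 0.5 SD in the stated direction; awareness could also act the other way. They should not be read as the trial's expected false-positive rate. If the PMC claim requires PMC to be worse than both comparators, the chance of a false claim from an equal shift in both real arms falls to about 1% to 2%. This is a cheap improvement to the design and its interpretation, not a flaw that invalidates the trial.

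**What to change.** - Describe the sham, including how it handles click and scalp sensation, and state who is blinded.
- Use one scripted instruction for all arms that does not reveal the arm.
- After the 30-minute retention block, record each participant's guessed condition and a 0-10 rating of scalp sensation and distraction during training. Asking earlier could prompt expectations before retention, which is itself a tested outcome.
- Report both by arm, descriptively. Do not treat a rating-adjusted estimate as evidence: the rating follows stimulation and may be closely tied to arm.
- Prespecify the PMC-sham and PMC-M1 contrasts alongside the ANOVA. Attribute a deficit specifically to PMC only if PMC is worse than both.
- State that a deficit against sham shared by both real arms cannot distinguish roles of both regions from a non-specific effect of real TMS. It should not be declared non-neural, because Aim 1 asks about both regions and genuine roles for both would give the same pattern.

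The cost is a few minutes per participant, one script and a few sentences in the plan. The guess is imprecise at 20 to 30 per arm and cannot prove blinding. The rating relies on recall over the retention interval. Requiring both contrasts lowers power relative to one, and the PMC-sham claim may have to be worded more cautiously.

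### The groups are to be matched on gender and age, but the primary one-way ANOVA leaves both factors out; adding them costs almost nothing and gains precision if either predicts the outcome.

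*Combined protocol and SAP*

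**What the plan says.** Under Experimental Design the protocol says that "participants will be randomly assigned to receive one of three types of stimulation during the motor learning paradigm", and shortly afterwards that "Groups will be gender- and age- matched". It does not say how the two go together: no stratification, minimisation or matched-set procedure is described.

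The Statistical Plan defines the outcome in two steps. First, "A skill score (SS) will be calculated as the difference between performance on the random blocks minus the average performance on the patterned sequence". Then, "Percent change in SS will be used to index sequence-specific motor learning while controlling for general improvements in motor performance". The control mentioned there comes from how the score is built (random against patterned blocks); it does not adjust for age or gender. The test is given as "One-way ANOVA will be used to test for differences in sequence-specific skill acquisition and sequence-specific skill retention between the groups". No covariate, stratum or blocking term is named for it anywhere.

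Group size is stated in two ways. Participants and Recruitment says "we anticipate that 30 participants per group (N=90 total) will provide sufficient power to test the primary study hypotheses", while Experimental Design lists "TMS over premotor cortex (N=20" and the same number for the other two groups. That conflict is a separate matter; the figures below are given for both sizes. The age span is wide: the Exclusion Criteria remove only people who "are outside the age range of 18-85".

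**The concern.** Matching on a factor that predicts the outcome makes the group means more alike in that factor, so their differences vary less from trial to trial. A model with group alone does not register this: the age- and gender-related spread remains in the residual mean square. The reported standard errors are then too wide and the F test rejects less often than its nominal 5%. The design pays for balance and the analysis does not collect the return.

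What is at stake is modest. The planned test keeps its own power and is not biased; the extra precision is forgone. This holds only if matching operates inside random allocation. The text also leaves room for placing participants by hand to reach balance, which would put the randomisation itself in question.

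**Working it through.** **Inputs from the documents.** Three groups; 30 per group (Participants and Recruitment) or 20 per group (Experimental Design); alpha 0.05 (Statistical Plan); ages 18-85.

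**Inputs assumed.** The documents give no effect size, SD, target power or explained variance, so the stated sample size cannot be reproduced.
- R² is the share of within-group outcome variance explained by age and gender together. It is taken from 0 to 20%, with 20% as an upper value.
- In the simulations, age is uniform on 18-85, gender is 50/50, age carries 80% of R² and gender 20%.
- One group is lower than the other two.
- f=0.333 is a benchmark, chosen because it gives 80% power at 30 per group. It is not a trial figure.

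**Step 1: benchmark power, group only.** The F test has 2 and N-3 degrees of freedom and noncentrality λ = N·f².
- N=90: λ = 90 × 0.333² = 9.98, power 80.0%.
- N=60: λ = 60 × 0.333² = 6.65, power 60.7%.

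**Step 2: why the group-only test is conservative.** Under perfect matching, the variance of a group difference is (1-R²) times what the residual mean square implies. The reported standard error is therefore too wide by √(1/(1-R²)): 1% at R²=0.02, 3% at 0.05, 5% at 0.10 and 12% at 0.20. The type I error is close to P(F > F_crit/(1-R²)). At N=90, F_crit(2, 87) = 3.10. For R²=0.20 the effective threshold is 3.10/0.80 = 3.88, which gives 2.4%. Simulation (400,000 trials per cell) agrees:

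| R² | Type I error, 20 per group | 30 per group |
|---|---|---|
| 0 | 5.01% | 5.04% |
| 0.02 | 4.68% | 4.72% |
| 0.05 | 4.31% | 4.28% |
| 0.10 | 3.64% | 3.69% |
| 0.20 | 2.48% | 2.47% |

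The adjusted model stayed between 4.6% and 5.3% in every cell.

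**Step 3: power with age and gender in the model.** Degrees of freedom become 2 and N-5, and λ = N·f²/(1-R²). At N=90 and R²=0.10, λ = 9.98/0.90 = 11.09 and power is 84.2%. At R²=0.20, λ = 9.98/0.80 ≈ 12.5 and power is 88.4%. Simulated power at f=0.333 under perfect matching (20,000 trials per cell), group-only / adjusted:

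| R² | 20 per group | Forgone | 30 per group | Forgone |
|---|---|---|---|---|
| 0 | 60.9 / 60.9 | 0.0 | 80.3 / 80.3 | 0.0 |
| 0.02 | 60.7 / 61.5 | 0.8 | 80.7 / 81.4 | 0.7 |
| 0.05 | 60.6 / 63.1 | 2.5 | 80.1 / 81.8 | 1.7 |
| 0.10 | 60.8 / 65.9 | 5.1 | 81.2 / 84.6 | 3.4 |
| 0.20 | 60.3 / 70.9 | 10.6 | 81.2 / 88.5 | 7.3 |

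Across f from 0.25 to 0.40 and both sizes, the loss is 0.3-1.1 points at R²=0.02, 0.8-2.6 at 0.05, 1.6-5.2 at 0.10 and 2.9-12.0 at 0.20.

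**Step 4: other ways of allocating.**
- *Stratified permuted blocks of three* (three age bands by gender). Group-only type I error is 4.5-4.6%, 3.6-4.0% and 2.8% at R² of 0.05, 0.10 and 0.20. Power forgone at f=0.333 is 1.8-2.7, 3.3-4.7 and 7.2-11.1 points.
- *Unconstrained allocation.* The group-only test is then at its nominal level. At f=0.333, group-only / adjusted power is 61.1 / 59.5 (20 per group) and 80.0 / 78.8 (30 per group) at R²=0; at R²=0.05 it is 60.8 / 61.4 and 80.1 / 81.1. Adjustment breaks even between 2% and 5% explained.

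**Step 5: how large R² could be.** The outcome is a percent change, so noise in the baseline skill score dilutes any relation with age or gender. If the two factors explain 20% of the absolute gain, they explain about 19, 17, 13 and 1% of the percent change at a baseline coefficient of variation of 0.1, 0.2, 0.3 and 0.5. Starting from 10%, the shares are 9, 8, 6 and 0.4%. This takes mean gain and SD of gain each as half of baseline, with baseline unrelated to age and gender. It shows direction only.

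**The case against.** The strongest reply is that nothing here is an error. The one-way ANOVA does not exceed its nominal level, and almost any unadjusted trial could gain from a prognostic covariate. The documents never claim that age or gender is prognostic. The skill score is a difference that should be small before the pattern is learned, so its relative spread at baseline may be large. The explained share of a percent change could then be 1% or less, at which even perfect matching yields under 1 point at the benchmark effect. If allocation turns out to be unconstrained, adjustment is a net loss at 0% explained (0.5-1.8 points) and still slightly negative at 2%. The count of two degrees of freedom also takes age as linear over 18-85; a curved form would cost more.

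All of this is accurate, and it limits the size of the point. It does not remove it. The protocol itself chose these two factors to balance on, and an analysis should reflect the balancing actually done. The unconstrained case disappears once the matching is carried out by stratified randomisation. The larger figures, including the 12.0-point maximum, belong to the upper end of an assumed range and should not be read as a forecast for this trial.

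**Conclusion.** The concern holds as a minor point of efficiency. The plan matches on gender and age and then analyses as if it had not. If matching is enforced within randomisation and the two factors explain 5-10% of the outcome variance, the group-only ANOVA runs at about 3.6-4.3% instead of 5% and forgoes roughly 2 to 5 points of power at f=0.333. Near 0% explained there is nothing to gain and almost nothing to lose. Explained variance and effect size are both assumptions, so the direction is firmer than the size. The conclusion is the same at 20 and at 30 per group.

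**What to change.** Replace the one-way ANOVA for acquisition and retention with an ANCOVA that has stimulation group, age (continuous) and gender, and fix the covariates and the form of age before any outcome data are seen. State that the matching is achieved by randomisation stratified by gender and age band, so that random assignment and matching are both true.

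The cost is two error degrees of freedom (57 to 55 at 20 per group, 87 to 85 at 30) and a stratified allocation list. No new data are needed: age is required for eligibility, and both factors for the matching. If neither factor is prognostic, power falls by less than 0.2 points under perfect matching and by 0.3-0.5 points with stratified blocks. Were allocation left unconstrained, it would fall by at most about 2 points.
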